The study, as detailed within this Research Protocol, will be conducted in accordance with the principles of GCP, the UK Policy Framework for Health and Social Care Research, and the Declaration of Helsinki and any other applicable regulations. I delegate responsibility for the statistical analysis and oversight to a qualified statistician (see declaration below).

CI Name: [name]

Signature:

Date: 08-07-2025

Statistician's Agreement

The study as detailed within this research protocol will be conducted in accordance with the current UK Policy Framework for Health and Social Care Research,, the World Medical Association Declaration of Helsinki (1996), Principles of ICH E6-GCP, ICH E9 - Statistical principles for Clinical Trials and ICH E10 - Choice of Control Groups.

I take responsibility for the statistical work in this protocol is accurate and take responsibility for statistical analysis and oversight in this study.

Statistician's name: [name]

Signature: [name].

Date: 08-07-2025

PeriCompass-31 Protocol | IRAS: 328971 | v1.0, 08.07.2025 Chief Investigator: [name]

3. Summary and synopsis

Short title	peri-Compass-31						
Methodology	Observational study						
Objectives	To provide a mechanistic understanding of why, and which elements of, autonomic dysfunction predisposes individuals to infectious and/or cardiovascular complications following major noncardiac surgery.						
Number of participants	296						
Inclusion and exclusion criteria	 Patients aged ≥ 50 years and over undergoing elective major noncardiac surgery under general anaesthesia expected to require at least an overnight stay in hospital. Exclusion criteria Inability or refusal to provide written informed consent. Inability to complete questionnaires. American Society of Anesthesiologists (ASA) score of I. 						
Study duration	24 months						

4. Introduction

4.1. Background

Experimental and clinical association studies show that autonomic dysfunction causes, augments, systemic inflammation,⁽¹⁾ infections,⁽²⁾ myocardial injury, (3) gastrointestinal complications⁽²⁾ and lung injury.⁽⁴⁾ As perioperative morbidity typically involves several organs, generalised loss of autonomic function is a plausible unifying pathological driver underlying infectious complications after major surgery. However, screening/ identifying autonomic dysfunction in patients before surgery is rather more challenging and has not been systematically explored at scale. The Composite Autonomic Symptom Score-31 (COMPASS-31) score may provide in-depth assessment of autonomic abnormalities in different organs before surgery. (5) This scale includes 31 questions pertaining to mainly six domains of sympathovagal imbalance dysfunction, such as gastrointestinal vasomotor imbalance, secretomotor disturbances, pupillomotor abnormalities, orthostatic intolerance, and urinary dysfunction. The total scoring if added, usually ranges between zero and 100, with a maximum score of 40 for orthostatic intolerance followed by 25 for gastrointestinal dysfunction, 15 for glandular abnormalities, and 10 for urinary ailments with five each for vasomotor and pupillomotor problems, respectively. The scale has an outstanding internal validity of 0.9. However, preoperative COMPASS-31 has not been examined or related to perioperative outcomes including infection and myocardial injury, common complications that prevents recovery and rehabilitation. Moreover, preoperative COMPASS-31 has not been validated against deliverable, objective measures of autonomic dysfunction including heart rate variability. (6)

4.2. Rationale

To provide a mechanistic understanding of why, and which elements of, autonomic dysfunction predisposes individuals to infectious and/or cardiovascular complications following major noncardiac surgery.

4.3. Risks / benefits

This is an observational study and will not involve any interventions that will influence patients care. Blood samples will be obtained at convenient times when routine blood tests are undertaken to minimise patient inconvenience.

5. Study objectives

5.1. Primary objective

 To identify an association between infectious complications and autonomic dysfunction using the preoperative Composite Autonomic Symptom Score-31 scores within 30 days after surgery.

5.2. Secondary objectives

 To identify an association between cardiovascular morbidity and autonomic dysfunction using the preoperative Composite Autonomic Symptom Score-31 scores within 30 days after surgery.

5.3. Mechanistic objectives

- To identify an association between heart rate variability and preoperative Composite Autonomic Symptom Score-31 within the first two days after surgery.
- To explore changes in whole blood proteomics associated with infectious complications 30 days from surgery.

5.4. Primary outcome measure

The primary outcome is the total COMPASS-31 score.

5.5. Secondary outcome measures

Individual components of the COMPASS-31 questionnaire: orthostatic intolerance, vasomotor, secretomotor, gastrointestinal, bladder, pupillomotor abnormalities.

5.6. Co-exposure of interest

The co-exposure of interest is:

- 1) Infectious complications within 30 days after surgery, a composite defined as one or more of the following infections of Clavien-Dindo grade II or greater. A full list of definitions is available in Appendix 1:
 - i. Superficial surgical site infection;
 - ii. Deep surgical site infection;
 - iii. Organ space surgical site infection;
 - iv. Pneumonia;
 - v. Urinary tract infection;
 - vi. Laboratory confirmed blood stream infection;
 - vii. Infection, source uncertain (antibiotics given on clinical suspicion).

2) Cardiovascular morbidity defined as one or more of Standardised Endpoints and Core Outcome Measures for Perioperative Medicine and Anaesthetic Care (StEP-COMPAC) cardiovascular complications: myocardial infarction, myocardial injury, cardiovascular death, non-fatal cardiac arrest, coronary revascularisation, major adverse cardiac events, pulmonary embolism, deep vein thrombosis, and atrial fibrillation AND/OR hypotension (mean arterial pressure <60mmHg) detected as part of routine clinical care requiring pressor infusion within 30 days after surgery.

5.7. Mechanistic outcome measures

- Myocardial injury by measuring plasma high sensitivity troponin-T (Elecsys, Roche Diagnostics) levels
- Continuous heart rate monitoring using Phillips CE-marked Holter device from the induction of anaesthesia and up to two days after surgery.
- Whole blood proteomic response to ex vivo inflammatory ligands (laboratory work for samples obtained at Royal London Hospital only).

5.8. Process measures

- Duration of hospital stay (number of days from surgery until a participant is medically fit to be discharged from the hospital)
- Critical care admission (level two or level three)
- Duration of critical care days (level two or level three)

6. Study population

During the trial recruitment period, hospital research teams will liaise with clinical staff to identify individuals with upcoming major noncardiac surgery that may be eligible for enrolment. Based on this referral, a member of the team delivering the trial at the hospital (e.g. clinician, nurse or research practitioner) with appropriate knowledge will formally assess eligibility of the participant against trial inclusion and exclusion criteria. No additional tests or investigations will be required for assessing eligibility.

6.1. Inclusion criteria

 Patients aged ≥ 50 years and over undergoing elective major noncardiac surgery under general anaesthesia expected to require at least an overnight stay in hospital.

Chief Investigator: [name]

6.2. Exclusion criteria

- · Lack of capacity or refusal to provide written informed consent
- Inability to complete questionnaires
- American Society of Anesthesiologists (ASA) score of I

7. Study design

Multi-centre observational cohort study across surgical services in NHS hospitals.

8. End of study

The end of the study is defined as the point when the last patient has completed the 30-day follow-up.

9. Study procedures

9.1. Screening and recruitment

Research delivery staff at each recruiting site should be regarded as part of the direct care team. Research is a routine part of effective healthcare and will be subject to the same information governance requirements in this respect. Potential participants will be identified via two routes: 1) the direct care team screening pre-admission clinic lists, operating theatre lists and by communication with the relevant nursing and medical staff or 2) pre-screening patients that have registered their interest in the study via a QR code located on the patient pamphlet. This process requires patients to provide their contact information (i.e. name, telephone number and email address) in a Microsoft form securely stored within QMUL. All patients registered using this method will undergo a further screening by a member of the direct care team to confirm eligibility prior to approach.

All patients who undergo screening will be recorded on the screening log and reasons given for any exclusion. Only anonymised screening data will be collected to allow assessment and reporting of selection bias. Once the participant has been enrolled, they will also be recorded on the study enrolment log together with their study ID. Both the screening and enrolment logs will be stored in the Investigator Site File (ISF).

9.2. Informed consent

The Principal Investigator (PI) has overall responsibility for the informed consent of participants at their site and will ensure that any person delegated responsibility to participate in the informed consent is duly authorised, trained and competent in obtaining informed consent. All staff taking consent will be trained in taking consent

and this will be evidenced on the local delegation log(s). They will also have appropriate Good Clinical Practice (GCP) training.

The consent process will take place face to face or via a locally approved remote method (phone, video conferencing etc.). All potential participants will be provided with a copy of the latest versions of the patient information sheet and informed consent form together with an explanation of the aims, methods, anticipated benefits and potential hazards of the trial. This will be done either in person (preferred), via email or by post. Where possible all patients will be given a minimum of 24 hours between the time they are approached about the study and the time when consent is given. Prior to consent a member of the research team will confirm how consent will be provided by the patient (face to face, email or post) and this will be documented on the informed consent form itself. For those patients who have not been contacted face-to-face, the signed consent form will be returned via email or by post and counter-signed a member of the research team.

For patients who are consented to participate in the study a copy of the patient information sheet and signed informed consent form will be filed in the medical notes. Patients who are consented but not entered into this study should be recorded (including reason not entered) on the screening log in the Investigator Site File. Original signed consent forms will be kept by the investigators and a copy will be given to the participant. The discussion and the consenting process will be documented in the patients' medical records.

If a participant loses capacity during their participation in the trial, the original consent by the participant will be respected. If this situation occurs, clinical outcome data will continue to be collected, but participant questionnaires will not need to be completed. The right of a patient to refuse participation without giving a reason will be respected. The participant will remain free to withdraw at any time from the study without giving reasons and without prejudicing their further treatment.

9.3. Follow-up procedures

Patients will be required to complete the COMPASS-31 questionnaire either face to face or remotely (e.g. phone, post, electronic). For those patients completing the questionnaire electronically, a link or QR code will be sent to them depending on their preference. Once the link has been used, the submitted answers cannot be modified.

Chief Investigator: [name]

Troponin-T will be measured in blood samples collected from venous or arterial catheters before anaesthesia induction and day one after surgery (10:00am ± 6 hours).

Heart rate using the Phillips CE-marked Holter device from before the induction of anaesthesia and up to three days postoperatively. The Holter monitor will be loaned to the sites by the Sponsor.

Participants' medical history will be reviewed to collect the details on surgery and 30-day follow-up which includes any infective and cardiovascular postoperative complications.

9.4. Study schedule

	Screening/		Day of	Postoperative					Hospital	30-day
Visit	Pre- screening	Before surgery	surgery (Day 0)	Day 1 [#]	Day 2 [#]	Day 3 [#]	Days 4-6	Day 7	discharge (days + 3 days)	follow-up + 7 days
Eligibility	х									
Informed consent		х								
Demographics		Х								
Review of medical notes		Х								
Data collection		Х	х	Х	Х	Х	Х	Х	х	Х
COMPASS 31										
questionnaire		X								
Heart rate monitoring			х	Х	Х					
Blood sample collection			X*	X***						
StEP-COMPAC			х	Х	Х	Х	Х	Х	х	Х
Post-operative infection										
(Clavien-Dindo Grade II			x	х	х	Х	Х	Х	x	х
and above)										
Other post-operative										
complications (Clavien-			x	x	×	x	x	v	x	Х
Dindo Grade II and			^	^	^	^	^	Х	^	^
above)										
Length of hospital stay										Х
Hospital readmission										Х

^{*} before start of surgery
*** morning after surgery

9.5. Study assessments

The following data will be collected from all patients:

Baseline data

- · Study ID
- Patient initials
- Date of consent and surgery
- Age
- Sex at birth
- Planned surgical procedure category
- Co-morbidities
- Frailty (Rockwood scale)
- Ethnicity (to calculate estimated glomerular filtration rate)
- · Index of socioeconomic deprivation.
- Laboratory values (haemoglobin, creatinine, neutrophil count, lymphocyte count, albumin)
- Continuous heart rate (measured with Holter monitor) up to three days following surgery
- Planned level of care on the first night after surgery

During surgery

- Start and end times of surgery
- Surgical procedure category (surgery involving the gut, all other surgery)
- Surgical technique (open, laparoscopic, laparoscopic converted to open)
- Anaesthetic technique (general anaesthesia, neuraxial, other regional anaesthesia, sedation)
- Volume of blood products administered (packed red cells, all other products)
- Continuous heart rate (measured with Holter monitor)

Follow-up data

30-day follow-up

- Mortality status within 30 days of surgery
- Clavien-Dindo graded infectious and all-cause complications within 30 days of surgery
- StEP-COMPAC defined cardiovascular complications within 30 days of surgery
- Number of days in level two and level three critical care within 30 days of surgery
- Duration of hospital stay

- · Critical care admission
- · Duration of critical care days

10. Statistical considerations

10.1. Sample size

296 patients are required to have a 90% chance of detecting, as significant at the 1% level, a mean difference in COMPASS-31 score of 5 (SD:8) between an estimated ~20% patients who develop postoperative infections, compared with patients who remain free of infection after surgery (STATA).

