10.2. Method of analysis

For the primary outcome, the absolute COMPASS-31 score will be compared between patients with/without infectious/cardiovascular complications (unpaired t-test). For secondary outcomes, individual components of the COMPASS-31 score, the presence/absence of individual components will be compared (Fisher exact test). Statistical analysis plans for both clinical and mechanistic studies will be published online before database closure.

11. Ethics

The Chief Investigator must ensure that the study is conducted in accordance with the guidelines of the International Conference on Harmonisation, GCP and UK legislation. All study documentation will be reviewed and approved by the research ethics committee prior to start of recruitment. Research Ethics Committee, Health Research Authority and Sponsor approvals will be in place before patient recruitment commences. The study will be sponsored by QMUL. Additionally, each participating site will ensure that the approval of the relevant trust Research & Development department and Ethics Committee is in place and a written confirmation is provided to the Sponsor.

12. Patient and Public Involvement (PPI)

The grant proposal for this study has been designed with the PPI members at The Patient, Carer & Public Involvement and Engagement (PCPIE) group at the Royal College of Anaesthetists. Furthermore, our PPI co-applicant have reviewed the protocol and will continue to advise us for the duration of the study including dissemination of the study results.

13. Data handling and record keeping

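### Section 10.1: the stated inputs need about 242 patients for 90% power, not 296; at 296 the power is about 95.6%, so the error is conservative but the sentence needs correcting

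*Protocol*

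**What the plan says.** Protocol section 10.1 is a single sentence. It gives the total, the power and the level ("296 patients are required to have a 90% chance of detecting, as significant at the 1% level, a mean difference in COMPASS-31 score"), the effect and spread ("a mean difference in COMPASS-31 score of 5 (SD:8"), and the comparison ("between an estimated ~20% patients who develop postoperative infections, compared with patients who remain free of infection after surgery (STATA"). Section 10.2 names the test: "the absolute COMPASS-31 score will be compared between patients with/without infectious/cardiovascular complications (unpaired t-test". The synopsis in section 3 repeats 296 as the number of participants.

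Section 10.1 does not say whether the test is one- or two-sided. It mentions no allowance for withdrawal, cancelled surgery or missing questionnaires, and 296 is presented as the number needed for the power itself.

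**The concern.** Apart from sidedness, section 10.1 supplies every input of a standard two-group calculation, so the total can be checked directly. It does not come out. The stated inputs lead to a clearly smaller total, and the stated total leads to a clearly higher power.

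This is the protocol's only power statement and the only place where a significance level appears. While its figures disagree, a reader cannot tell what the study was designed to detect, how much room it has for lost patients, or how low the infection rate may fall before power drops below 90%. Those answers depend on which inputs were really used.

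**Working it through.** **Inputs (section 10.1, test from section 10.2).** Difference 5, SD 8, so d = 5/8 = 0.625. Infected share p = 0.20. Level 0.01. Power 0.90. Unpaired t-test. Assumption: two-sided.

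**Step 1. Try to reproduce 296 by the normal approximation.**

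N = (z₀.₉₉₅ + z₀.₉₀)² / [d² p(1 − p)] = (2.576 + 1.282)² / (0.625² × 0.16) = 14.879 / 0.0625 = 238.1

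That is 239 patients, or 240 as 48 + 192. The stated 296 is not reproduced.

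**Step 2. Exact t-test.** Power comes from the noncentral t distribution with N − 2 degrees of freedom and noncentrality λ = d √[N p(1 − p)].

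| Calculation with the stated inputs | Total N for 90% power |
|---|---|
| Equal-variance t, 20:80 split | 242 (power 90.1%; 241 gives 89.9%) |
| Equal-variance t, whole numbers 49 + 196 | 245 (power 90.5%) |
| Welch t | 250 |
| Equal-variance t, one-sided 1% | 212 |

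A one-sided reading moves further from 296. Inflating 242 for a rank test gives 253 (factor π/3) to 280 (dividing by 0.864). The protocol names a t-test, and neither figure reaches 296.

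**Step 3. Power at the stated total.** λ = 0.625 × √(296 × 0.16) = 0.625 × 6.882 = 4.301. At the two-sided 1% level:

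- equal-variance t: 95.6% (95.5% with 59 + 237);
- Welch t: 95.0%;
- normal approximation: 95.8%.

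**Step 4. Size of the gap.** 296 − 242 = 54 patients, and 296/242 = 1.22. Against Welch it is 296 − 250 = 46 patients, and 296/250 = 1.18.

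**Step 5. What would make 296 right?** Each line changes only what it names; the test is the equal-variance t unless Welch is given.

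| Change | Value that gives 296 |
|---|---|
| Difference | about 4.5 instead of 5 |
| SD | about 8.9 instead of 8 |
| Infected share | about 15.4% instead of 20% (15.5% gives 295) |
| Unstated loss allowance | 1 − 242/296 = 18% |
| Power and level | 99% power at two-sided 5%: smallest N is exactly 296 |
| Power only, Welch | 95% power at two-sided 1%: smallest N is exactly 296 |

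Six different changes reach the same total, so the total alone does not identify the cause.

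**The case against.** The best defence is that the discrepancy does no harm. It runs in the safe direction: on the stated assumptions the study has more power than it claims. The study is observational, section 4.3 says it will not influence care, and blood is taken alongside routine tests, so extra patients carry little burden. This stands, and it limits the seriousness of the point.

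A second defence is that the approximation sign before 20%, or a tacit allowance for losses, covers the gap. It does not. The infection rate would have to be about 15.4%, and even a 1:5 split (16.7% infected) needs 282 with the equal-variance t-test; it comes near 296 (294) only with Welch. An allowance may have been intended, but none is written, and the sentence ties 296 directly to the power.

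A reader might infer two stronger things. One is that the primary test was really planned at 5%, because 296 is exactly the total for 99% power at that level, so that a p-value between 0.01 and 0.05 would have an unclear status. The documents do not support this. The protocol gives 1% and nowhere mentions 5%. The 5% reading comes only from working backwards, and 95% power at 1% under Welch fits equally well while keeping the stated level. The other inference is that the study is the wrong size. The stated inputs show it to be larger than they require, not too small.

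**Conclusion.** The total and the power in section 10.1 do not follow from the inputs beside them. With a two-sided 1% test, difference 5, SD 8 and 20% infected, 90% power needs about 242 patients (250 with Welch), and 296 patients give about 95.6% (95.0% with Welch). The stated total is 22% above what the inputs require, or 18% with Welch.

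The conclusion assumes a two-sided test, a common SD, a 20:80 split and complete data on all patients counted. A one-sided test would widen the gap. The cause cannot be settled from the document: the total, power, level, SD, difference, infection rate or an undisclosed loss allowance could each be the item mis-stated or left out. The study is not underpowered on its own assumptions. This is a reporting error that should be fixed, with no reason to change recruitment.

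**What to change.** Keep 296. Retrieve the original Stata command and correct section 10.1 to agree with it.

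- If the stated inputs are the ones intended, write: *296 evaluable patients give about 95.6% power at the two-sided 1% level to detect a difference of 5 (SD 8) with 20% infected; about 242 would give 90%.*
- If a different level, power, SD, difference or infection rate was used, or a loss allowance was planned at the time, state that instead.
- Do not add an attrition figure merely because it closes the gap. The 18% above is back-calculated and has no source in the protocol.

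In section 10.2, state the confirmed significance level and sidedness of the primary test.

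The cost is a look at the original calculation, one corrected sentence in section 10.1 and one added in section 10.2. Recruitment and data collection do not change.
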